6.0 TRIAL FLOW CHART

6.1 Study Flow Chart

Trial Period:	Screening Phase	Treatment Cycles ^b								End of Treatment	Post-Treatment		
		1	2	3	4	To be repeated beyond 8 cycles					DC	Safety Follow-up ^c	Follow Up Visits ^d
Treatment Cycle/Title:	Screening (Visit 1) ^a					5	6	7	8	DC	30 days after last dose (±3 days)	Every 9 or 12 weeks (±7 days)	Every 12 weeks (±7 days)
Scheduling Window (Days):	-42 to -1		±3	±3	±3	±3	±3	±3	±3	At time of DC			
Administrative Procedures													
Informed Consent	X ^f												
Informed Consent for FBR (optional)	X												
Inclusion/Exclusion Criteria	X												
Subject Identification Card	X (dispense)									X (collect)			
Demographics and Medical History	X												
Prior and Concomitant Medication Review	X ^g	X	X	X	X	X	X	X	X	X	X ^g		
Trial Treatment Administration		X ^h	X	X	X	X	X	X	X				
Subsequent Anticancer Therapy Status												X	X
Survival Status ⁱ		←-----→									←-----→		X
Clinical Procedures/Assessments													
AE/SAE Monitoring	X	X	X	X	X	X	X	X	X	X	X ^j	X ^j	
Full Physical Examination ^k	X									X			
Directed Physical Examination ^k		X	X	X	X	X	X	X	X				
Vital Signs and Weight ^l	X	X	X	X	X	X	X	X	X	X			
12-Lead ECG	X												
ECOG Performance Status	X	X	X	X	X	X	X	X	X ^m	X			
Laboratory Procedures/Assessments: analysis performed by LOCAL laboratory													
PT/INR and PTT/aPTT	X ⁿ												
CBC with Differential ^o	X ⁿ		X	X	X	X	X	X	X	X	X ^p		
Comprehensive Chemistry Panel ^o	X ⁿ		X	X	X	X	X	X	X	X	X ^p		
Urinalysis ^{o,q}	X ⁿ		X ^q		X		X		X	X	X ^p		
T3, FT4 and TSH ^o	X ⁿ		X ^q		X		X		X	X	X ^p		

Trial Period:	Screening Phase	Treatment Cycles ^b								End of Treatment	Post-Treatment		
		1	2	3	4	To be repeated beyond 8 cycles					DC	Safety Follow-up ^c	Follow Up Visits ^d
Treatment Cycle/Title:	Screening (Visit 1) ^a					5	6	7	8				
Scheduling Window (Days):	-42 to -1		±3	±3	±3	±3	±3	±3	±3	At time of DC	30 days after last dose (±3 days)	Every 9 or 12 weeks (±7 days)	Every 12 weeks (±7 days)
Total Testosterone ^o	X ⁿ				X ^r				X	X			
Laboratory Procedures/Assessments: analysis performed by CENTRAL laboratory													
Tumor Marker Assessment (PSA) ^s	X				X			X		X		X	
PSA for Cohorts 4 and 5 ^s	X		X	X	X			X		X		X	
Anti-drug Antibodies (ADA) ^t		X	X		X			X		X			
Pembrolizumab Pharmacokinetics (serum) ^t		X ^u	X		X			X		X			
Blood for CTC		X ^{v, w}								X			
Blood for AR-V7 ^v		X											
Efficacy Measurements													

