- d. Follow-up visits must occur using the same imaging schedule the subject was on during treatment (eg, every 9 weeks [63 days ±7 days] from the date of allocation or every 12 weeks [84 days ±7 days] from the date of allocation). In subjects who discontinue study therapy without documented disease progression, every effort should be made to continue monitoring their disease status by radiologic imaging (CT/MRI and bone scans) and PSA according to the schedule that the subject was on at the time of discontinuation (eg, every 9 or 12 weeks from the date of allocation) until: 1) the start of new anti-cancer treatment, 2) documented disease progression, 3) death or 4) the end of the study, whichever occurs first.
- e. Survival follow-up begins 12 weeks from the time a subject experiences confirmed disease progression or starts a new anti-cancer treatment.
- f. Written consent must be obtained prior to performing any protocol specified procedures. Results of a test performed prior to the subject signing consent are acceptable in lieu of new screening tests if they are a part of routine clinical management and performed within the specified timeframe.
- g. Prior medications: record all medications taken within 28 days prior to the first dose of trial treatment. Concomitant medications: enter new medications started during the trial and up to 30 days after last dose of trial treatment regardless of when the safety follow-up visit occurs. All medications related to reportable SAEs and events of clinical interest (ECIs) should be recorded as defined in Section 7.2.
- h. Trial treatment should begin on the day of treatment allocation or as close as possible to the date on which the subject is allocated, ie, ≤7 days.
- i. After documented local site assessed disease progression, or the start of new anticancer treatment; contacts are approximately every 12 weeks by telephone. Updated survival status may be requested by the Sponsor at any time during the course of the study. Upon Sponsor notification, all participants who do not/will not have a scheduled study visit or study contact during the Sponsor defined time period will be contacted for their survival status (excluding participants that have a death event previously recorded).

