- j. Record all AEs (including ECIs) occurring up to 30 days after the last dose of trial treatment. SAEs must be recorded up to 90 days after the last dose of trial treatment or 30 days following cessation of treatment if the subject starts new anti-cancer treatment. Treatment related SAEs must always be reported.

Trial Period:	Screening Phase	Treatment Cycles ^b								End of Treatment	Post-Treatment			
		1	2	3	4	To be repeated beyond 8 cycles					DC	Safety Follow-up ^c	Follow Up Visits ^d	Survival Follow-Up ^e
Treatment Cycle/Title:	Screening (Visit 1) ^a					5	6	7	8					
Scheduling Window (Days):	-42 to -1		±3	±3	±3	±3	±3	±3	±3	±3	At time of DC	30 days after last dose (±3 days)	Every 9 or 12 weeks (±7 days)	Every 12 weeks (±7 days)

- k. A full physical exam will be performed at screening and at treatment discontinuation; all treatment visits will include a directed physical exam.
- l. Height will be measured at screening only.
- m. Following Cycle 8, ECOG Performance Status will be performed at every other cycle (Cycles 10, 12, 14,...) and at treatment discontinuation.
- n. Laboratory procedures at screening are to be performed within 10 days prior to the first dose of trial treatment.
- o. After Cycle 1, pre-infusion laboratory procedures may be conducted up to 72 hours pre-infusion.
- p. Unresolved abnormal lab results associated with drug-related AEs should be followed until resolution.
- q. Urinalysis and thyroid function testing are done at screening, every other cycle (Cycles 2, 4, 6,...), treatment discontinuation, and the safety follow-up visit.
- r. Total testosterone will be done at screening, every fourth cycle (Cycles 4, 8, 12,...) and at treatment discontinuation
- s. Imaging assessments (CT/MRI and bone scans) and PSA should be performed every 9 weeks (63 days ±7 days) for the first year (through week 54), every 12 weeks (84 days ±7 days) in the second year, at treatment discontinuation and during follow-up. The timing of these assessments should not be adjusted for dose delays or cycle starts. For Cohorts 4 and 5, screening PSA by central results are required prior to allocation. PSA should be performed Q3W until Cycle 4.
- t. Pre-infusion (trough) PK and anti-pembrolizumab antibody (ADA) samples will be collected within 24 hours before infusion at Cycles 1, 2, 4, 6, and 8. To be collected from subjects in Cohorts 1 to 3 only.

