7.1.5.3.1 Survival Follow-up

Subjects who experience confirmed disease progression or start a new anticancer therapy, will move into the Survival Follow-Up Phase and should be contacted by telephone approximately every 12 weeks to assess for survival status until death, withdrawal of consent, or the end of the trial, whichever occurs first. The Sponsor may request survival status be assessed at additional time points during the course of the study. For example, these additional time points may be requested prior to an efficacy interim analysis and/or final analysis. All subjects who are not known to have died prior to the request for these additional survival status time points will be contacted at that time.

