7.1.5.4 Survival Status

To ensure current and complete survival data is available at the time of database locks, updated survival status may be requested during the course of the study by the Sponsor. For example, updated survival status may be requested prior to but not limited to an external Data Monitoring Committee (eDMC) review, interim and/or final analysis. Upon Sponsor notification, all participants who do not/will not have a scheduled study visit or study contact during the Sponsor defined time period will be contacted for their survival status (excluding participants that have a previously recorded death event in the collection tool).

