All adverse events that occur after the consent form is signed but before treatment allocation/randomization must be reported by the investigator if they cause the subject to be excluded from the trial, or are the result of a protocol-specified intervention, including but not limited to washout or discontinuation of usual therapy, diet, placebo treatment or a procedure. From the time of treatment allocation/randomization through 30 days following cessation of treatment, all adverse events must be reported by the investigator. Such events will be recorded at each examination on the Adverse Event case report forms/worksheets. The reporting timeframe for adverse events meeting any serious criteria is described in section 7.2.3.1. The investigator will make every attempt to follow all subjects with non-serious adverse events for outcome.

Electronic reporting procedures can be found in the Electronic Data Capture (EDC) data entry guidelines. Paper reporting procedures can be found in the Investigator Trial File Binder (or equivalent).

Adverse events will not be collected for subjects during the pre-screening period (for determination of archival tissue status) as long as that subject has not undergone any protocol-specified procedure or intervention. If the subject requires a blood draw, fresh tumor biopsy etc., the subject is first required to provide consent to the main study and AEs will be captured according to guidelines for standard AE reporting.

7.2.1 Definition of an Overdose for This Protocol and Reporting of Overdose to the Sponsor

For purposes of this trial, an overdose will be defined as any dose exceeding the prescribed dose for pembrolizumab defined as any dose greater than 1000 mg or greater. No specific information is available on the treatment of overdose of pembrolizumab. In the event of overdose, pembrolizumab should be discontinued and the subject should be observed closely for signs of toxicity. Appropriate supportive treatment should be provided if clinically indicated.

If an adverse event(s) is associated with (“results from”) the overdose of Sponsor's product or vaccine, the adverse event(s) is reported as a serious adverse event, even if no other seriousness criteria are met.

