Progression-free-survival (rPFS) is defined as the time from first day of study treatment to the documented disease progression by central imaging vendor where PD in bone-only tumors will be determined by radionuclide bone scan using PCWG3 criteria and PD for all other tumors will be determined using RECIST 1.1 or death due to any cause, whichever occurs first.

- **Overall Survival (OS)**

Overall survival (OS) is defined as the time from first day of study treatment to the time of death.

- **Duration of PSA response (Cohorts 4 and 5 only)**

Duration of PSA response is defined as the time from PSA response, when the PSA value first declines by at least 50% of the baseline (must be confirmed by a second value), to the date of PSA progression at which there is an increase of 25% or more from the nadir PSA, provided the absolute increase from the nadir PDA is at least 2 ng/mL.

- **Time to initiation of cytotoxic chemotherapy (Cohorts 4 and 5 only)**

Time to initiation of cytotoxic chemotherapy is defined as the time from first day of study treatment to the time of initiation of cytotoxic chemotherapy for prostate cancer.

- **Time to new-anticancer therapy (Cohorts 4 and 5 only)**

Time to new-anticancer therapy is defined as the time from first day of study treatment to the time of new-anticancer therapy for prostate cancer

- **Time to first skeletal-related event (Cohorts 4 and 5 only)**

Time to initiation of first skeletal-related event is defined as the time from first day of study treatment to the first skeletal-related event, which is defined as radiation therapy or surgery to bone, pathologic bone fracture, spinal cord compression, or change or antineoplastic therapy to treat bone pain. See Section 8.6.1 for censoring rules.

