Time to first skeletal-related event	Summary statistics using Kaplan-Meier method	ASaT in 
 • Cohorts 4 and 5 • Cohort 4 • Cohort 5 	Censored at last date known alive

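### Time to first skeletal-related event is censored at last date known alive, although no ascertainment of these events is scheduled in survival follow-up

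*Protocol*

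**What the plan says.** Time to first SRE is a secondary objective for Cohorts 4 and 5 (Protocol 3.2). Protocol 8.4.1 defines it as a composite that includes "radiation therapy or surgery to bone, pathologic bone fracture, spinal cord compression" and a change of antineoplastic treatment for bone pain. It sends the reader to 8.6.1 for censoring. The only SRE rule there is the Table 9 cell, "Censored at last date known alive", and sSAP Table 3 repeats it.

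The collection schedule after treatment is as follows.

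- Subjects enter survival follow-up at confirmed progression or new anticancer therapy. They "should be contacted by telephone approximately every 12 weeks to assess for survival status until death" (Protocol 7.1.5.3.1). The flow chart footnote agrees: "contacts are approximately every 12 weeks by telephone".
- The Survival Follow-Up column of the flow chart is marked for "Subsequent Anticancer Therapy Status" and for survival status. The AE/SAE row is blank there.
- Before database locks, "updated survival status may be requested during the course of the study by the Sponsor" (Protocol 7.1.5.4). No other question is attached to that contact.
- Protocol 7.2 on adverse events: "From the time of treatment allocation/randomization through 30 days following cessation of treatment, all adverse events must be reported by the investigator". For serious events, "SAEs must be recorded up to 90 days after the last dose of trial treatment" (flow chart footnote j), shortened to 30 days if new therapy starts. Only treatment-related SAEs stay reportable afterwards.

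**The concern.** Censoring at last date known alive is valid only if event status is known up to that date. Table 9 mostly respects this. PSA progression and rPFS are censored at last assessment. OS needs only vital status. The two therapy-initiation endpoints can lean on the therapy-status item in the survival column. SRE is the row whose censoring date can run past any scheduled ascertainment.

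A man who progresses, moves to telephone follow-up and then has a vertebral fracture may be confirmed alive for another year. If the fracture is not recorded, that year enters the Kaplan-Meier risk set as SRE-free time. The error can go only one way, towards a longer SRE-free time. At stake is how a reader interprets a published SRE-free curve from a trial without a comparator.

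**Working it through.** **Which components have a route after the AE/SAE window**

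| SRE component | Stated route in survival follow-up |
|---|---|
| Radiotherapy or surgery to bone | Partial: Protocol 5.6.2 requires these to be recorded while on study, a term not defined for this phase |
| Change of antineoplastic therapy for bone pain | Partial: new therapy is reviewed (7.1.1.5.4), but recording the reason is not required |
| Pathologic fracture | None, unless a treatment-related SAE |
| Spinal cord compression | None, unless a treatment-related SAE |

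**Size, on assumed rates.** The documents state no SRE rate, event count or capture rate, so there is no figure to reproduce. Assume independent exponential times, with full capture until survival follow-up starts and for *d* months after that. A share *c* of later SREs is captured. If last date known alive is unrelated to SRE risk, the plan's rule estimates the distribution of recorded SREs and treats the unrecorded ones as never happening:

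reported 12-month rate = 1 − [c·F + (1 − c)·A]

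Here F = 1 − e^(−12λ) is the true probability of an SRE by 12 months. A is the probability of an SRE by 12 months that falls inside the collection period:

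A = (1 − e^(−λd)) + e^(−λd) · λ/(λ+μ) · (1 − e^(−(λ+μ)(12−d)))

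Inputs:

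- True SRE median 12 months (assumed): λ = ln2/12 = 0.0578, F = 0.50.
- Median time to survival follow-up 4.1 months (a PFS median quoted in Protocol 4.2.1, used only as an anchor) or 8 months (assumed): μ = ln2/4.1 = 0.1691, or ln2/8.
- *d* = 30 or 90 days, the AE and SAE windows, counted for simplicity from the start of survival follow-up.
- Optional six-week delay added to *d*, because entry needs confirmed progression and bone progression is confirmed at least 6 weeks later (Protocol 7.1.2.6.2).

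First row: d = 30/30.44 = 0.986. A = 0.0553 + 0.9447 × 0.2547 × (1 − 0.0822) = 0.276. With c = 0 the reported rate is 1 − 0.276 = 72.4%. With c = 0.5 it is 1 − (0.25 + 0.138) = 61.2%.

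| Median to survival follow-up, window | Delay | None captured | Half | Three quarters | All |
|---|---|---|---|---|---|
| 4.1 months, 30 days | none | 72.4% | 61.2% | 55.6% | 50.0% |
| 4.1 months, 90 days | none | 65.6% | 57.8% | 53.9% | 50.0% |
| 8 months, 30 days | none | 64.4% | 57.2% | 53.6% | 50.0% |
| 8 months, 90 days | none | 59.7% | 54.9% | 52.4% | 50.0% |
| 4.1 months, 30 days | 6 weeks | 67.5% | 58.8% | 54.4% | 50.0% |
| 4.1 months, 90 days | 6 weeks | 61.5% | 55.8% | 52.9% | 50.0% |
| 8 months, 30 days | 6 weeks | 61.0% | 55.5% | 52.8% | 50.0% |
| 8 months, 90 days | 6 weeks | 57.0% | 53.5% | 51.8% | 50.0% |

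A simulation with 400,000 subjects per setting agrees within 0.2 points. Ignoring censoring, the sampling standard error is √(0.5 × 0.5/120) = 4.6 points for both cohorts together and √(0.5 × 0.5/40) = 7.9 points for Cohort 5. The bias is 3.5 to 11.2 points at half capture and 1.8 to 5.6 points at three quarters.

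**The case against.** The strongest reply is that this argues from silence. Neither flow chart has an SRE row at any visit, even on treatment, so a blank in the survival column does not show that collection stops there. Case report form details lie outside these documents: Protocol 7.2 points to data entry guidelines and 10.6 to separate data management procedures. Protocol 5.8.1 also requires data on clinical events after discontinuation to be collected through the last scheduled follow-up. Part of this stands. The case report form may capture some later SREs, and a reader should not infer that all are lost. But 5.8.1 names no SRE and defers to the flow chart and 7.1.5.3, which schedule none in this phase.

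A reader might also infer that SREs are lost even on treatment, because progression is exempt from AE and SAE reporting (7.2, 7.2.3.3). The documents do not support a rate for this. For stopping treatment, 5.8.1 does not count clinical deterioration as progression, and 7.2.3.3 sends suspected endpoints found not to be progression to safety reporting. No reduced early capture is therefore assumed above.

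The size is also open to challenge. The 4.1-month anchor comes from a retrospective study. Waiting for confirmed progression shortens the unobserved period, and at three-quarters capture most settings then fall within one standard error. That is why the delayed settings are in the table.

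**Conclusion.** The mismatch is real and minor. The plan's censoring date can extend past any scheduled ascertainment of fracture and cord compression, and any resulting bias favours longer SRE-free time. Its size cannot be derived from the documents. The ranges above rest on assumed exponential rates, full early capture, and a last-known-alive date unrelated to SRE risk. The 57.0% to 72.4% range needs zero later capture, which the documents do not establish.

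Two wider readings should be resisted. The trial's main conclusions are not in doubt: ORR, rPFS and OS do not use SRE data, and Protocol 8.8 plans no hypothesis test. Nor is last date known alive wrong for the two therapy-initiation endpoints as such, since the 12-weekly contacts collect therapy status. The extra contacts under 7.1.5.4 mention survival only, so for those endpoints the rule is acceptable only where therapy status was asked at that contact.

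**What to change.** **Main change, Cohorts 4 and 5.** State in Protocol 7.1.5.3.1 and the flow chart that SRE status is recorded at scheduled visits and at the existing 12-weekly contacts. Record type, date, and the reason for any radiotherapy, surgery or therapy change, whether or not the event is judged to be progression. In Protocol Table 9 and sSAP Table 3, censor subjects without an SRE at the last contact at which SRE status was asked.

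**Where the question was not asked.** This includes contacts already made; these cohorts date from Amendment 03 (2017) and the current text is Amendment 07 (2021). Censor at the last clinic visit within the AE/SAE collection window. Keep the current rule as a sensitivity analysis that counts later recorded SREs. Report the lower precision and the possible informative censoring.

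**Therapy-initiation endpoints.** Keep last date known alive only where therapy status was asked at that contact; otherwise use the last contact where it was.

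**Cost.** The main change adds a few form fields and questions to existing contacts. In 2,000 simulated trials of 120 subjects (the four no-delay settings, SRE median 12 months), its standard error was 5.2 to 5.8 points, against 5.1 to 5.6 for the current rule with full capture. The fallback, modelled as censoring at the 30-day safety visit, had 6.7 to 10.3 points. Its root-mean-square error (6.7 to 10.3) beats the current rule at no later capture (10.8 to 22.7), is mixed at half (6.9 to 12.2) and loses at three quarters (5.6 to 7.7). If SRE risk doubles after on-study observation, the fallback leaves about 8 to 11 points of bias. Use it only where the question was not asked.

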8.6.2 Statistical Methods for Safety Analyses

Safety will be summarized for the overall safety population for Cohorts 1, 2, and 3 in the post-chemotherapy population and overall safety for Cohorts 4 and 5 in the pre-chemotherapy population. If there is no difference among individual patient populations, an overall analysis will be performed.

Safety and tolerability will be assessed by clinical review of all relevant parameters including adverse experiences (AEs), laboratory tests, and vital signs. Count and percentage of AE will be provided.

Summary statistics (counts, percentage, mean, standard deviation, etc.) will be provided for the safety endpoints as appropriate. The summary statistics of count and percentage will be provided for the incidence rate of any AE, any serious AE, any Grade 3-5 AE, any drug-related AE, any serious and drug-related AE, any Grade 3-5 and drug-related AE, dose interrupted due to AE, discontinuation due to AE, any immune-related AE (irAE), death and specific AEs.

The summary statistics of mean and standard deviation will be provided for change from Baseline Results (Labs and Vital Signs) within each treatment cycle. The summary statistics of count and percentage will be provided for laboratory worsening from Baseline in terms of CTCAE grades.

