5.2.1.2 Dose Modification (Escalation/Titration/Other)

5.2.1.2.1 Pembrolizumab

Dose modification and toxicity management for immune-related AEs associated with pembrolizumab

AEs associated with pembrolizumab exposure may represent an immunologic etiology. These immune-related AEs (irAEs) may occur shortly after the first dose or several months after the last dose of pembrolizumab treatment and may affect more than one body system simultaneously. Therefore, early recognition and initiation of treatment is critical to reduce complications. Based on existing clinical trial data, most irAEs were reversible and could be managed with interruptions of pembrolizumab, administration of corticosteroids, and/or other supportive care. For suspected irAEs, ensure adequate evaluation to confirm etiology or exclude other causes. Additional procedures or tests such as bronchoscopy, endoscopy, or skin biopsy may be included as part of the evaluation. Based on the severity of irAEs, withhold or permanently discontinue pembrolizumab and administer corticosteroids. Dose modification and toxicity management guidelines for irAEs associated with pembrolizumab are provided in [Table 3](#).

Table 3 Dose Modification and Treatment Discontinuation Guidelines for Immune-related Adverse Events Associated with Pembrolizumab

General instructions:				

 1. Corticosteroid taper should be initiated upon AE improving to Grade 1 or less and continue to taper over at least 4 weeks. 2. For situations where pembrolizumab has been withheld, pembrolizumab can be resumed after AE has been reduced to Grade 1 or 0 and corticosteroid has been tapered. Pembrolizumab should be permanently discontinued if AE does not resolve within 12 weeks of last dose or corticosteroids cannot be reduced to ≤ 10 mg prednisone or equivalent per day within 12 weeks. 3. For severe and life-threatening irAEs, IV corticosteroid should be initiated first followed by oral steroid. Other immunosuppressive treatment should be initiated if irAEs cannot be controlled by corticosteroids. 				
irAEs	Toxicity grade or conditions (NCI CTCAE v4.0)	Action taken to pembrolizumab	irAE management with corticosteroid and/or other therapies	Monitor and follow-up

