7.2.3 Immediate Reporting of Adverse Events to the Sponsor

7.2.3.1 Serious Adverse Events

A serious adverse event is any adverse event occurring at any dose or during any use of Sponsor's product that:

- Results in death;
- Is life threatening;

- Results in persistent or significant disability/incapacity;
- Results in or prolongs an existing inpatient hospitalization;
- Is a congenital anomaly/birth defect;
- Is an other important medical event.

Note: In addition to the above criteria, adverse events meeting either of the below criteria, although not serious per ICH definition, are reportable to the Sponsor in the same timeframe as SAEs to meet certain local requirements. Therefore, these events are considered serious by the Sponsor for collection purposes.

- Is a new cancer (that is not a condition of the study);
- Is associated with an overdose.

Refer to [Table 7](#) for additional details regarding each of the above criteria.

For the time period beginning when the consent form is signed until treatment allocation/randomization, any serious adverse event, or follow up to a serious adverse event, including death due to any cause other than progression of the cancer under study (reference Section 7.2.3.3 for additional details), that occurs to any subject must be reported within 24 hours to the Sponsor if it causes the subject to be excluded from the trial, or is the result of a protocol-specified intervention, including but not limited to washout or discontinuation of usual therapy, diet, placebo treatment or a procedure.

For the time period beginning at treatment allocation/randomization through 90 days following cessation of treatment, or 30 days following cessation of treatment if the subject initiates new anticancer therapy, whichever is earlier, any serious adverse event, or follow up to a serious adverse event, including death due to any cause other than progression of the cancer under study (reference Section 7.2.3.3 for additional details), whether or not related to the Sponsor's product, must be reported within 24 hours to the Sponsor either by electronic media or paper. Electronic reporting procedures can be found in the EDC data entry guidelines. Paper reporting procedures can be found in the Investigator Trial File Binder (or equivalent).

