8.4.2 Safety Endpoints

The primary safety objective of this trial is to characterize the safety and tolerability of pembrolizumab in subjects with mCRPC. The primary safety analysis will be based on subjects who experienced toxicities as defined by CTCAE criteria. Safety will be assessed by quantifying the toxicities and grades experienced by subjects who have received pembrolizumab, including serious adverse events (SAEs) and events of clinical interest (ECIs).

Safety will be assessed by reported adverse experiences using CTCAE, Version 4.0. The attribution to study treatment, time-of-onset, duration of the event, its resolution, and any concomitant medications administered will be recorded. AEs will be analyzed including but not limited to all AEs, SAEs, fatal AEs, and laboratory changes.

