### 3.6.2 Statistical Methods for Safety Analyses

Safety will be summarized for the overall safety population for Cohorts 1, 2, and 3 in the post-chemotherapy population and overall safety for Cohorts 4 and 5 in the pre-chemotherapy population. If there is no difference among individual patient populations, an overall analysis will be performed. Safety and tolerability will be assessed by clinical review of all relevant parameters including adverse experiences (AEs), laboratory tests, and vital signs. Counts and percentages of AE will be provided.

Summary statistics (counts, percentages, means, standard deviations, etc.) will be provided for the safety endpoints as appropriate. The summary statistics of count and percentage will be provided for the incidence rate of any AE, any serious AE, any Grade 3-5 AE, any drug-related AE, any serious and drug-related AE, any Grade 3-5 and drug-related AE, dose interrupted due to AE, discontinuation due to AE, any immune-related AE (irAE), death and specific AEs of interest.

The summary statistics of mean and standard deviation will be provided for change from Baseline Results (Labs and Vital Signs) within each treatment cycle. The summary statistics of count and percentage will be provided for laboratory worsening from Baseline in terms of CTCAE grades.

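### AE and irAE summaries are planned only as crude percentages, with no allowance for time under observation, so they can create or mask a difference between Cohorts 1-3 and Cohorts 4-5

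*Protocol*

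**What the plan says.** The planned AE summaries are the same in both documents. Protocol section 8.6.2 says: "The summary statistics of count and percentage will be provided for the incidence rate of any AE, any serious AE, any Grade 3-5 AE". The list continues through drug-related events, interruptions and discontinuations. In sSAP section 3.6.2 it ends with "any immune-related AE (irAE), death and specific AEs of interest". Both sections report the post-chemotherapy Cohorts 1-3 and the pre-chemotherapy Cohorts 4-5 separately, and both call for an overall analysis if the populations do not differ. Neither defines what counts as no difference.

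The dates needed for a time-based summary are collected. Protocol section 8.4.2 says: "The attribution to study treatment, time-of-onset, duration of the event, its resolution, and any concomitant medications administered will be recorded". No analysis of onset or duration is specified in either document. Kaplan-Meier methods are planned for efficacy endpoints only.

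Time matters for this class of event. Protocol section 5.2.1.2.1 says: "These immune-related AEs (irAEs) may occur shortly after the first dose or several months after the last dose of pembrolizumab treatment". Observation time also varies widely. Treatment runs from a single infusion to 35 cycles, and Protocol section 7.2 sets the general AE window: "From the time of treatment allocation/randomization through 30 days following cessation of treatment, all adverse events must be reported by the investigator". For serious events, section 7.2.3.1 extends it: "For the time period beginning at treatment allocation/randomization through 90 days following cessation of treatment", or 30 days after treatment if new anticancer therapy starts earlier.

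Extent of exposure (Protocol section 8.11, sSAP section 3.12) is a count of cycles for the treated population. It is not stated to be by cohort and is not linked to AEs.

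**The concern.** A subject who stops early and has no irAE within the collection window stays in the denominator as irAE-free, with the same weight as a subject observed for two years. The percentage therefore reflects how long subjects stay on treatment as well as how toxic the treatment is per month. The text calls the result an incidence rate, but it is a proportion.

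This matters most where the plan sets the two populations side by side. They differ in treatment history, so different treatment durations are possible. Safety for all cohorts combined and by cohort is the first secondary objective (Protocol section 3.2), and the overall analysis in section 8.6.2 depends on judging that the populations do not differ. That judgement could go wrong either way: a difference caused only by exposure, or a real difference hidden by it.

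**Working it through.** The documents give no irAE rate, no expected treatment duration and no planned safety figure, so there is nothing to reproduce. The figures below illustrate size under stated assumptions.

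**Inputs from the documents.** Maximum treatment is 35 cycles of 3 weeks, 35 × 3 = 105 weeks, about 24 months. The general AE window adds 30 days, about 1 month. Planned sizes are 200 + 50 = 250 for Cohorts 1-3 and 80 + 40 = 120 for Cohorts 4-5.

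**Assumptions.** Constant irAE hazard h per month, identical in both populations. Time on treatment T is exponential with mean m months, capped at 24. Observation lasts T + 1 months.

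**Formula.** With a = 1/m + h:

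E[exp(-hT)] = ((1/m)/a) × (1 - exp(-24a)) + exp(-24a)

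crude percentage = 1 - exp(-h) × E[exp(-hT)]

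**Worked cases at h = 0.02.**
- m = 3: a = 0.3533, E = 0.9434, crude = 1 - 0.9802 × 0.9434 = 7.5%.
- m = 9: a = 0.1311, E = 0.8540, crude = 1 - 0.9802 × 0.8540 = 16.3%.

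| Monthly hazard | m = 3 | m = 4 | m = 6 | m = 9 | 12-month risk, 1 - exp(-12h) |
|---|---|---|---|---|---|
| 1% | 3.9% | 4.8% | 6.5% | 8.7% | 11.3% |
| 2% | 7.5% | 9.2% | 12.4% | 16.3% | 21.3% |
| 4% | 14.2% | 17.2% | 22.4% | 28.7% | 38.1% |

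At 2%, the artificial ratio is 9.2/7.5 = 1.2 for 4 against 3 months, 16.3/12.4 = 1.3 for 9 against 6, 12.4/7.5 = 1.65 for 6 against 3, and 16.3/7.5 = 2.2 for 9 against 3. With equal exposure it is 1.0.

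**Masking.** This uses the same type of model, with medians in place of means, a cap of 105 weeks and a 30-day window. A hazard of 5% per month with median treatment of 3 months gives 21.7%. A hazard of 3% with median 6 months gives 22.3%. The percentages look alike although one hazard is 5/3 = 1.7 times the other.

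**Does fixed-time incidence remove the artefact?** With a common hazard of 3% and medians of 3 and 6 months, the crude percentages are 14.1% and 22.3%. Simulation (4,000 runs, n = 250 and 120, no competing deaths) gives Kaplan-Meier 6-month incidences of 16.5% and 16.4%, against a true 1 - exp(-0.18) = 16.5%.

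**Do exposure-adjusted rates remove it?** Only if the hazard is constant. Take an identical front-loaded hazard in both populations: 4% per month for 4 months, then 0.5%.
- Expected events per subject = 0.04 × [1 + m(1 - exp(-3/m))] + 0.005 × m[exp(-3/m) - exp(-24/m)].
- Expected person-months = m(1 - exp(-24/m)) + 1.
- m = 3: (0.04 × 2.896 + 0.005 × 1.103)/4.00 = 0.1214/4.00, or 3.0 per 100 person-months.
- m = 9: (0.04 × 3.551 + 0.005 × 5.823)/9.37 = 0.1712/9.37, or 1.8 per 100 person-months.

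That is a false ratio of about 1.7, pointing the opposite way to the crude percentages (11.3% and 15.6%). Incidence at a fixed time is the same in both populations here, for example 1 - exp(-(0.16 + 0.01)) = 15.6% at 6 months.

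**The case against.** The strongest reply is that this is a descriptive Phase II study. Protocol section 8.8 rules out hypothesis testing. A crude percentage correctly describes what was seen during the collection window. Section 3.2 already requires safety for all cohorts combined and by cohort, so little turns on the pooling sentence. Exposure is summarised, and the wording of sections 8.4.2 and 8.6.2 leaves room for further statistics. Serious events are followed to 90 days, and section 7.2.3.1 makes related serious events reportable at any time.

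Much of this stands, and it limits how much weight the point can bear. It does not remove the point. Permission to add summaries is not a plan to do so. A cycle count that is neither by cohort nor linked to AEs cannot correct a percentage. The longer reporting of serious events does not cover non-serious irAEs.

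Stronger readings are tempting but unsupported:
- A reader might infer that onset is recorded because irAEs can be delayed. Section 8.4.2 covers all AEs and gives no reason; the remark on delay belongs to the dose-modification guidance.
- A reader might infer that the populations will show a false difference. The documents give no treatment duration by cohort, so neither the size nor the direction is known.
- A reader might take a ratio near 2 as typical. It needs mean exposures as far apart as 3 and 9 months; 4 against 3 months gives about 1.2.

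**Conclusion.** The point holds as a gap in the analysis plan. Crude percentages are the only AE incidence summaries named, and the judgement on pooling has no allowance for time under observation. Under an equal constant hazard of 2% per month, the artificial ratio between populations ranges from 1.0 (equal exposure) to about 2.2 (mean treatment of 9 against 3 months). A real hazard ratio of 1.7 can also disappear. These sizes rest on assumed hazards and exponential treatment times. The mechanism needs only unequal observation time.

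The primary endpoint, sample size and ORR intervals are unaffected. Nor would a better summary let a reader attribute a difference to enzalutamide: the cohorts are nonrandomised and differ in prior treatment. This is a cheap improvement, not a flaw that undermines the trial.

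**What to change.** In Protocol section 8.6.2 and sSAP section 3.6.2, keep the counts and percentages and add the following, by population:

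1. For irAEs and for Grade 3-5 drug-related AEs, the cumulative incidence of the first event at fixed times, for example 3, 6 and 12 months from first dose. Treat death as a competing event and censor at the end of the AE collection window of the first treatment course. State which window applies, since all AEs have 30 days and serious events up to 90.
2. Median and range of time to onset and of duration for the same events.
3. Extent of exposure by cohort.
4. A statement that the judgement of no difference between populations rests on the cumulative incidence, with the criterion given.

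Exposure-adjusted rates may be shown as a supplement but should not be the sole basis for comparison, because they mislead when the hazard is not constant.

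The cost is SAP wording and one or two extra tables from dates already collected. Intervals will be wide at late times, when few subjects remain under observation. The estimate assumes that stopping treatment is unrelated to the subject's later irAE risk. Non-serious irAEs that start after the 30-day window remain uncounted, and the report should say so.
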